APPENDIX 1: BRIGHTON COLLABORATION CASE DEFINITION OF ANAPHYLAXIS³⁵

Anaphylaxis is a clinical syndrome characterized by:

- sudden onset AND
- rapid progression of signs and symptoms AND
- involving multiple (≥2) organ systems, as follows:

Level 1 of diagnostic certainty
 
 • ≥1 major cardiovascular AND/OR ≥1 major respiratory criterion AND • ≥1 major dermatological criterion

Level 2 of diagnostic certainty
 
 • ≥1 major cardiovascular AND ≥1 major respiratory criterion OR • ≥1 major cardiovascular OR respiratory criterion AND • ≥1 minor criterion involving ≥1 different system (other than cardiovascular or respiratory systems) OR • (≥1 major dermatologic) AND (≥1 minor cardiovascular AND/OR minor respiratory criterion)

Level 3 of diagnostic certainty
 
 • ≥1 minor cardiovascular OR respiratory criterion AND • ≥1 minor criterion from each of ≥2 different systems/categories

Note that all levels of diagnostic certainty **require the involvement the cardiovascular and/or respiratory systems.**

Organ System	Major Criteria	Minor Criteria
Skin or mucosal	
 • generalized urticaria (hives) or erythema • angioedema, localized or generalized • generalized pruritus with skin rash 	
 • generalized pruritus without skin rash • generalized prickle sensation • localized injection site urticaria • red and itchy eyes
Cardiovascular	
 • measured hypotension OR • shock (at least 3 of the following): 
 ▪ tachycardia ▪ capillary refill time (CRT) >3 sec ▪ reduced central pulse volume ▪ decreased level or loss of consciousness 	
 • Reduced peripheral circulation (at least 2 of: 
 • Tachycardia • CRT >3 sec without hypotension • Decreased level of consciousness
Respiratory	
 • Bilateral wheeze (bronchospasm) • Stridor • Swelling of upper airways • Respiratory distress (at least 2 of tachypnoea; use of accessory respiratory muscles; recession; cyanosis; grunting) 	
 • Persistent dry cough • Hoarse voice • Difficulty breathing without wheeze or stridor • Sensation of throat closure
Gastrointestinal		
 • Diarrhoea • Abdominal pain • Nausea • Vomiting
Laboratory		Mast cell tryptase > upper normal limit

NB: For the purposes of this study, local rhinitis and oropharyngeal symptoms will be classed as LOCAL symptoms and not indicative of a systemic allergy response.

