
Symptom(s)/sign(s) of 1 organ system present*
 
Cutaneous Generalized pruritus, urticaria, flushing, or sensation of heat or warmth†
 
or
 
Angioedema (not laryngeal, tongue or uvular)
 
or
 
Upper respiratory Rhinitis - (eg, sneezing, rhinorrhea, nasal pruritus and/or nasal congestion)
 
or
 
Throat-clearing (itchy throat)
 
or
 
Cough perceived to originate in the upper airway, not the lung, larynx, or trachea
 
or
 
Conjunctival Erythema, pruritus or tearing
 
Other Nausea, metallic taste, or headache
	
Symptom(s)/sign(s) of more than 1 organ system present
 
or
 
Lower respiratory Asthma: cough, wheezing, shortness of breath (eg, less than 40% PEF or FEV₁ drop, responding to an inhaled bronchodilator)
 
or
 
Gastrointestinal Abdominal cramps, vomiting, or diarrhea
 
or
 
Other Uterine cramps
	
Lower respiratory Asthma (eg, 40% PEF or FEV₁ drop NOT responding to an inhaled bronchodilator)
 
or
 
Upper respiratory Laryngeal, uvula, or tongue edema with or without stridor
	
Lower or upper respiratory Respiratory failure with or without loss of consciousness
 
or
 
Cardiovascular Hypotension with or without loss of consciousness
	
Death

SERIOUS ADVERSE EVENT REPORTING

Serious adverse events and reactions must be reported to the PIs within 24 hours. An SAE/SUSAR form should be completed and faxed to the study coordination centre for all SAEs within 24 hours. This will then be communicated to the IDMC Chair, ISC chair and study sponsor. In the event of serious adverse reaction (expected), reporting should also include using the yellow card system.

In the case of suspected unexpected serious adverse reactions (SUSARS), the staff at the site should:

[figure not shown]
Complete the SAE case report form & send it immediately (within 24 hours, preferably by email or fax), signed and dated to the study coordination centre together with relevant treatment forms and anonymous copies of all relevant investigations.

Or

Contact the study coordination centre by phone and then send the completed SAE form to the study coordination centre within the following 24 hours as above.

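### The Appendix 1 note that calls oropharyngeal symptoms local has no limit and is not reconciled with the anaphylaxis criteria or WAO Grade 3, leaving the anaphylaxis and systemic-only counts open to interpretation

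*Protocol*

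**What the plan says.** The Protocol section on grading and attribution of allergic reactions brings in two systems. WAO criteria determine and grade allergic reactions, and the Brighton case definition in Appendix 1 defines anaphylaxis.

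- **Note at the end of Appendix 1:** for this study, "local rhinitis and oropharyngeal symptoms will be classed as LOCAL symptoms and not indicative of a systemic allergy response".
- **Brighton table in the same appendix:** "Swelling of upper airways" is a major respiratory criterion. "Sensation of throat closure" and hoarse voice are minor respiratory criteria. "angioedema, localized or generalized" is a major skin or mucosal criterion. The definition is of a syndrome "involving multiple (≥2) organ systems, as follows", and all levels of certainty "require the involvement the cardiovascular and/or respiratory systems".
- **WAO table:** Grade 3 includes "Laryngeal, uvula, or tongue edema with or without stridor". The Grade 1 upper-respiratory entries are rhinitis, throat clearing or itchy throat, and cough of upper-airway origin.
- **Outcome and sample size:** the primary outcome is any immediate allergic reaction within 2 hours. The 0.5% statement in Sample Size Estimation assumes that 730 children have neither systemic nor significant local reactions. The same section words the earlier study's result as no systemic reactions in 433 doses.

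**The concern.** The note decides whether an event is local or systemic, yet nothing bounds it. Tongue and uvula are oropharyngeal in ordinary usage, and a sensation of throat closure is a throat symptom. The tables treat these findings as respiratory criteria for anaphylaxis or as Grade 3 signs, while the note, read literally, calls them local. No sentence says which prevails, so two assessors who both follow the Protocol can classify the same child differently.

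The literal reading errs in one direction: it lowers the anaphylaxis and systemic counts. It can also affect seriousness, because the allergic-reaction grading section treats mild as equivalent to non-anaphylactic and classes such events as non-serious. In a single-arm study that hopes to report zero events, a choice made after an event has been seen would not be credible.

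**Working it through.** **1. Reproduce the plan's figures.** Inputs: n = 730 and n = 433 with zero events (Sample Size Estimation). The exact two-sided 95% upper limit for zero events is 1 − 0.025^(1/n).

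- n = 730: 1 − 0.025^(1/730) = 0.504%, against the stated 0.5%.
- n = 433: 1 − 0.025^(1/433) = 0.848%, against the stated bound of 0.85%.

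The arithmetic is sound. The question is which events enter the count.

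**2. Apply the rules to three hypothetical children.** Sudden onset and rapid progression are assumed.

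| Findings | Brighton table alone | WAO table | Brighton table with the note read literally |
|---|---|---|---|
| A. Uvula swelling and generalised urticaria | Level 1: major respiratory plus major dermatological | Grade 3 | Throat sign is local and only skin remains; no level met |
| B. Throat-closure sensation, generalised itch without rash, vomiting | Level 3: minor respiratory plus minor criteria from two other systems | At least Grade 2 | Respiratory element is local; no level met |
| C. Tongue oedema alone | Not anaphylaxis, taken as one organ system | Grade 3 | Not anaphylaxis, and now local rather than systemic |

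A and B leave the anaphylaxis count. C leaves a systemic-only count. All three remain immediate allergic reactions under WAO, so all three stay in the primary outcome.

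**3. How often the local label will be used.** Study Justification reports 8 children with possible local symptoms among 282 children and 433 doses. Assuming a similar rate in 730 children, 730 × 8/433 = 13.5 and 730 × 8/282 = 20.7, so roughly 13 to 21 events. The earlier eight were all mild, so the gap matters only for the rare event that is not.

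**4. Illustration for the 0.5% statement.** This applies only if an event such as C is called local and also judged not significant. For one event the exact upper limit p solves (1 − p)^730 + 730p(1 − p)^729 = 0.025, which gives p = 0.761%. The limit moves from 0.50% to 0.76%.

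**5. Illustration for the historical comparison.** With one event in 730 and none in 433, the only two possible tables have probabilities 730/1163 = 0.628 and 433/1163 = 0.372. The two-sided Fisher p-value is their sum, 1. With 282 children as the comparator, 730/1012 + 282/1012 is also 1. What one reclassified event changes is the statement that neither study saw a systemic reaction, not the p-value.

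**The case against.** The strongest reply is that the adjective local may govern both rhinitis and oropharyngeal symptoms, and that the note speaks of symptoms, not swelling. It would then cover only mild contact effects such as an itchy throat, which are WAO Grade 1, and there would be no conflict. This shows that the passages are not a flat contradiction. It does not settle the matter. On that reading the note says that local symptoms are local, without saying which ones are. Throat-closure sensation is also a symptom in the strict sense, and it is a Brighton criterion.

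A reader might infer that the note can turn a true anaphylaxis into a non-event and so rescue the 0.5% claim. The Protocol does not support this. The primary outcome takes any immediate reaction. The 0.5% statement includes significant local reactions. Child A still has generalised urticaria, which the note does not touch. Symptoms requiring anaphylaxis treatment are serious adverse reactions whatever the note says, although that safeguard depends on treatment rather than on the sign observed. Central classification by WAO would still give tongue or uvula oedema Grade 3.

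A reader might also see a second conflict in nose-plus-eye symptoms, which are local in part under the note but Grade 2 under "Symptom(s)/sign(s) of more than 1 organ system present". This is not a contradiction. WAO grade and the local/systemic label are different axes, and one event can carry both.

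Finally, Study Justification words the earlier result more widely, as no systemic or significant local reactions. The historical comparison is exposed only if the narrower wording in Sample Size Estimation is used.

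**Conclusion.** The point holds as an unbounded and unreconciled classification rule. What it exposes is the Brighton anaphylaxis count, any systemic-only count and its comparison with the earlier study, and the non-serious label for events that are not called anaphylaxis. The primary outcome is not exposed. The 0.5% statement is exposed only through the undefined word significant; if one event were lost that way, the upper limit would be 0.76% rather than 0.50%. That size rests on a hypothetical single event, and the Protocol gives no rate for throat oedema after this vaccine. The conclusion also assumes that oropharyngeal includes tongue, uvula and throat. Laryngeal oedema arguably falls outside the term, and the case does not depend on it.

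**What to change.** Reconcile the Appendix 1 note with the Brighton and WAO tables before any event is classified:

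- Limit the note to the symptoms in the WAO Grade 1 upper-respiratory entries.
- State that it does not displace any Brighton respiratory criterion or any WAO Grade 3 sign.
- State that events with such findings count among the systemic or significant local reactions in Sample Size Estimation.

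Leave the WAO scale as it stands. Exempting nose-plus-eye symptoms from Grade 2 would rewrite the scale and lower the grade of events.

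The cost is two or three sentences, with no new data collection. The small downside is that a borderline throat symptom may count against a zero-event result.

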APPENDIX 2: TOPIC GUIDE FOR 72HR TELEPHONE FOLLOW-UP

Participants' families will be contacted by the local research team at least 72 hours after LAIV administration (and within 7 days, to allow for weekends), to determine whether their child has experienced any delayed symptoms which might be attributable to the vaccine. This telephone consultation will take approximately 2-3 minutes. If after three attempts (on three separate days) the local study team is unable to contact the family, the child will be deemed lost to follow up.

Guide to telephone interview:

1. Confirm interviewee's identity

2. Introduce yourself:

"I am <name>, from the SNIFFLE-2 Study. We arranged to speak briefly today to find how <participant's name> is going after his/her 'flu vaccine on <date>"

3. *"Have you noticed any health problems since the vaccine?"*

4. For each symptom reported:

- *When did this start?*
- *How long did this last?*
- *Did you do anything as a result?*

APPENDIX 3: TOPIC GUIDE FOR TELEPHONE FOLLOW-UP AT 4 WEEKS

**** For patients with asthma/recurrent wheeze only ****

Participants' families will be contacted by the local research team between 4-5 weeks after LAIV administration, to determine whether their child has experienced any change in their lower respiratory symptoms which might be attributable to the vaccine. This telephone consultation will take approximately 2-3 minutes. If after three attempts (on three separate days) the local study team is unable to contact the family, the child will be deemed lost to follow up.

Guide to telephone interview:

1. Confirm interviewee's identity
2. Introduce yourself:

"I am <name> from the SNIFFLE-2 Study. Your child <participant's name> had the 'flu vaccine with us one month ago, and we arranged to speak to find out if you had needed to do anything different with his asthma/wheezing"
3. Complete appropriate Asthma Control Questionnaire over the telephone

(see separate questionnaires)
4. Finally, ask the following questions:
 - i) *Since the vaccine, have you had to take <participant's name> to see a Doctor because of his/her breathing?*
 - ii) *(If YES) – did you have to take them to hospital?*
 - iii) *(If YES) – did <participant's name> have to stay in hospital overnight?*
